7.4.5.8 Penn spasm frequency scale (PSFS)

Key references Priebe et al 1996⁶⁰ and Penn et al 1985⁶¹

Self-reported measure that assesses an individual's perception of spasticity frequency and severity.

- Legs scored together

Scoring: The Penn Spasm frequency Scale is comprised of two parts:

- Part 1 - spasm frequency and
- Part 2 - spasm severity.

Instructions for carrying out the test

Self-reported outcome measure. See outcome measure sheet for instructions and criteria.

A score is awarded based on the criteria below

Part 1 – Spasm frequency

Level	Description
0	No spasms
1	Mild spasms induced by stimulation
2	Infrequent full spasms occurring less than once per hour
3	Spasms occurring more than once per hour
4	Spasms occurring more than 10 times per hour

Part 2 – Spasm severity

Level	Description
1	Mild
2	Moderate
3	Severe

7.4.6 Clinical measures and exercise testing

7.4.6.1 Lower limb range of movement ROM (Knee and ankle)

Instructions adapted from Tidy's physiotherapy 2003 – Musculoskeletal assessment – Chapter 11 ⁶²

Required equipment (clinician)

- Goniometer
- In some cases visual estimation maybe used e.g.
 - Where the position of the limb is at easily recognizable range of movements such as fully extended = 0°, bent to 90° etc
 - where the range of movement for active is the same as the passive range of movement visual estimation maybe used

Instructions for carrying out the test

- These may be conducted with the participant sitting.
- If a plinth, bed or appropriate piece of equipment is present that allows the participant to lie down in a suitable position for carrying out the measurements.
- The test may be done for up to maximum of 3 times for each movement.
- Active range of movement is completed by the participant moving the joint as much as possible using their own muscles.
- Passive range of movement is completed by the researcher or practitioner moving the joint of the participant as much as possible.

7.4.6.2 Assessing knee ROM

Active range of motion

- The **axis** of the goniometer should be positioned over the lateral femoral condyle.
- The **static arm** should be parallel with the long axis of the femur towards the greater trochanter.
- The **dynamic arm** should be positioned parallel to the long axis of the fibula and lateral malleolus
- Measurements to be conducted for
 - Extension

- Flexion
- If the participant can hyper extend this should be reported as a negative value e.g. -5°

[figure not shown]

Image taken from OrthoFixar.com

Passive range of motion

- For each of the respective movement the limb should be taken to the end of its available range.
- Using the same axis and arm locations above measure the passive range of movement.
- Measurements to be conducted for
 - Extension
 - Flexion

7.4.6.3 Assessing ankle ROM

- The **axis** of the goniometer is placed just inferior to the lateral malleolus.
- The **static arm** should be parallel to the fibula.
- The **dynamic arm** should be parallel to the long axis of the fifth metatarsal
- Measurements to be conducted for
 - Plantarflexion
 - Dorsiflexion
- The neutral or 0° position of the ankle is determined with the ankle in an orthogonal or 90° to the shank participant
- Values for plantar flexion and dorsiflexion are reported as positive i.e. 10°

[figure not shown]

Image adapted from Lutgens & Hamilton, 1997⁶³

Passive range of motion

- For each of the respective movement the limb should be taken to the end of its available range.
- Using the same axis and arm locations above measure the passive range of movement.
- Measurements to be conducted for
 - Plantarflexion
 - Dorsiflexion

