7.1.2 Exclusion Criteria

- Clinically isolated syndrome.
- People with MS in an active relapse or <8 -weeks since a relapse.
- Lower-limb peripheral nerve injury.
- Fixed lower-limb contractures.
- Contraindications to SNMES.
 - Pregnancy
 - Uncontrolled Epilepsy
 - Any of the following in the lower limbs
 - Peripheral nerve injury
 - Unstable fractures or orthopaedic condition affecting the lower limb
 - Cancer (malignancy) in the areas of the electrode placement
 - Skin infection / devitalised skin at the electrode placement site

- Unable to apply and control SNMES device or braces independently or with carer assistance.
- Other co-morbidities that could affect mobility/additional underlying condition e.g. stroke.

Cardiac pacemaker/history of cardiac problems will not be a reason for exclusion, but recruitment will be subject to cardiologist approval.

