7.4.4.4 Level of impairment (Walking aids)

Researcher to identify walking aids used

Walking aid	Tick
Independently mobile - no walking aids	
1 x walking stick (Fisher stick / cane)	
1 x elbow crutch	
2 x walking sticks (canes)	
2 x elbow crutches	
Rollator frame	
Zimmer frame	
Wheeled zimmer frame	
Ankle & foot orthosis (AFO) - single leg	
Ankle & foot orthosis (AFO) - bilaterally	
Functional electrical stimulation (FES) - single leg	
Functional electrical stimulation (FES) - bilaterally	
3 wheeled walker	
Gutter frame	
Gutter rollator frame	
Other (please state)	

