7.4.6.7 Timed up and Go (clinical measure)

Adapted from Podzialdo and Richardson 1991 ⁴⁵

Required equipment (clinician)

- stopwatch
- a chair that can be easily moved along the walking course
- 3.5 m hallway
- 30 m walkway

Location

- The Timed up and Go should be performed indoors, along a long, flat, straight, enclosed space with a hard surface. For the test, avoid corridors or spaces that are busy, used by lots of other people and have a high volume of footfall.
- Place a standard height chair at the beginning of the walkway

[figure not shown]

Image taken from Emerson Sebastião et al 2016 ⁴⁶

Measurement (carrying out the test)

- A “warm-up” period before the test is not required.
- A practice round may be performed if required but ensure that the participant has adequate time after this to recover.
- The participant should sit at rest in a chair, located near the starting position, for at least 10 minutes before the test starts.
- During this time make sure that clothing and shoes are appropriate.

Instructions for carrying out the test

1. The participant should sit on a standard armchair, placing their back against the chair and resting their arms chair's arms.
2. The upper extremities should not be on the assistive device (if used for walking), but it should be nearby.
3. Regular footwear and customary walking aids should be used.
4. Instruct the participant as follows:

- *The aim of this test is to assess the way you walk and balance.*
- *The test will start when I say Go.*
- *From sitting you will stand up, walk to the line/ cone that is 3 meters way, turn around at the line/cone walk back to the chair and sit down.*
- *I will stop the timer when your buttocks touch the seat*
- *The aim of the test is to see how fast you can do this but “You should walk at a comfortable and safe walking speed.”*

5. Demonstrate the test to the participant.
6. A stopwatch should be used to time the test (in seconds).
7. When the participant is ready say

“Go”

8. Start the stopwatch

9. Do not talk to anyone during the walk. Use an even tone of voice if required to instruct the participant.

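### The ankle-range rule has no code for dorsiflexion that stops short of neutral, and the Timed Up and Go script mixes two pace instructions

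*Protocol*

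**What the plan says.** **Ankle.** Section 7.4.6.3 fixes the zero point: "The neutral or 0° position of the ankle is determined with the ankle in an orthogonal or 90° to the shank". Its only rule on sign follows: "Values for plantar flexion and dorsiflexion are reported as positive i.e. 10". It says nothing about a maximum dorsiflexion that does not reach the zero point.

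The knee section just before it, 7.4.6.2, does use a sign for crossing zero: "If the participant can hyper extend this should be reported as a negative value e.g. -5". Section 7.4.6.1 has both active and passive range measured, and of the active test it says "Active range of movement is completed by the participant moving the joint as much as possible using their own muscles".

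**Who may be affected.** The exclusion list has "Fixed lower-limb contractures". The walking-aid form in Section 7.4.4.4 has tick boxes for "Ankle & foot orthosis (AFO) - single leg", for bilateral orthoses, and for functional electrical stimulation on one or both legs. Tibialis anterior is among the muscles stimulated (Section 7.4.8).

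**Timed Up and Go (TUG).** The script in Section 7.4.6.7 has one bullet with two halves joined by *but*: "The aim of the test is to see how fast you can do this", then "You should walk at a comfortable and safe walking speed".

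**Use of the data.** Table 1 has joint range and TUG at baseline, 12 weeks and 6 months. Sections 5.1 and 9.2.1 use the candidate outcomes to choose the primary outcome of a future trial and to calculate its sample size.

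**The concern.** With zero at neutral, dorsiflexion has two sides: past neutral and short of it. A rule that makes every value positive, with no exception, gives the two sides the same number. At the knee the protocol keeps them apart; at the ankle it does not.

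The case is foreseeable. A participant with weak dorsiflexors and no fixed contracture may fail to reach neutral actively, and the study stimulates the muscle that would change this. A deficit recorded without its sign would distort the level, change and SD of ankle range. A later analysis could not recover the sign from the stored number alone.

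The TUG point is separate. A fastest-pace and a comfortable-pace instruction ask for different effort. Participants know whether they have the device or only the booklets, so pace left to the participant could shift between visits for reasons unrelated to function.

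**Working it through.** **No planned figure depends on this.** The sample of 50 rests on the precision of three proportions. The half-width 1.96 × √(p(1−p)/n) gives 9.8, 11.1 and 15.2 points for (p, n) = (0.5, 100), (0.8, 50) and (0.6, 40). These match the stated 10, 11 and 15, and no ankle or TUG value enters them.

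**Literal reading: the sign is dropped.** Let a be the true signed dorsiflexion before and b after, negative meaning short of neutral. True change is b − a; recorded change is |b| − |a|.

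| True before → after | True change | Recorded before → after | Recorded change |
|---|---|---|---|
| −10 → −5 | +5 | 10 → 5 | −5 |
| −10 → 0 | +10 | 10 → 0 | −10 |
| −5 → +5 | +10 | 5 → 5 | 0 |
| −10 → +10 | +20 | 10 → 10 | 0 |
| −5 → +10 | +15 | 5 → 10 | +5 |

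- Level: for a < 0 the error is |a| − a = 2|a|, so 20° for a foot 10° short.
- Foot at or below neutral at both visits: recorded change = −(true change), a reversal.
- Foot crossing neutral (a < 0 < b): recorded change = b − |a|. This is zero when b = |a|, and has the right sign but too small a size when b > |a|.

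**Direction-convention reading: each movement is positive in its own direction, and the rule is silent on deficits.** The same true change from −10 to −5 is then +5 if the assessor writes negatives, 0 if the assessor writes 0 at both visits, and missing if the assessor leaves blanks. The protocol does not choose among these.

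**Effect on an SD carried forward (illustration only).** The protocol gives no ankle data, so these inputs are assumed: true dorsiflexion normal, mean m of −5°, 0°, 5° or 10°, SD s of 6°, 8° or 10°, and a 5° difference at 90% power and two-sided 5%. Under the literal reading the recorded value is folded normal:

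- mean M = s√(2/π)·exp(−m²/2s²) + m(1 − 2Φ(−m/s))
- SD = √(m² + s² − M²)
- n per arm = 2(1.960 + 1.282)² × SD² / 5², rounded up

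| True SD | Recorded SD over the four means | n per arm, true SD | n per arm, recorded SD |
|---|---|---|---|
| 6° | 3.62–5.58 | 31 | 11–27 |
| 8° | 4.82–6.87 | 54 | 20–40 |
| 10° | 6.03–7.99 | 85 | 31–54 |

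Worked case, m = 0 and s = 8: M = 6.38, SD = √(64 − 6.38²) = 4.82, n = 20 against 54. Across the grid the assumed share below neutral runs from 4.8% to 79.8%, which shows how far the result depends on inputs that the protocol does not supply. The 5° difference is held fixed; sign loss would distort that as well.

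**TUG.** There is nothing to compute. Set beside the Two-minute walk test script in 7.4.6.8, which asks for maximum distance without running, the TUG bullet gives a speed aim and a comfort instruction together. The walk test shows that the protocol can state one clear task.

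**The case against.** The strongest reply is that the ankle sentence follows directly on the definition of neutral and reads naturally as a direction convention. The rule is then silent on deficits, not wrong, and a sensible assessor might write a negative value. The goniometry figure is not shown, and the outcome measure and clinical test pack listed in Appendix 1 may already give a code. This stands, and it limits the claim. It does not close the gap, because silence still allows different coding by different assessors at two sites.

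A reader might infer that a foot short of neutral is stored as normal dorsiflexion. The text does not say so and gives no normal range. A reader might also infer that change is reversed for everyone below neutral. Even on the literal reading that is true only while the foot stays at or below neutral: −5° to +5° records no change, and −5° to +10° keeps its direction. Nor does the walking-aid form show that foot drop is common. It is a general tick-list, and a listed option is not a prevalence. Excluding fixed contractures makes a passive deficit rarer at entry, though it leaves active weakness and restriction that develops during follow-up.

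On TUG, the word *but* arguably subordinates the timed aim to the comfortable pace, and Section 6 has activities the same at both sites. That softens the conflict. Participants still hear both halves, and a common script carries the ambiguity to both sites. That SNMES participants will walk faster at follow-up is speculation; an effort effect could arise in an open-label study under any wording.

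Finally, ankle range is one of many candidate measures. The study aim names weakness, walking, fatigue and quality of life, not joint range.

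**Conclusion.** The point holds in a limited form. The ankle rule has no code for dorsiflexion short of neutral. Taken literally, it cannot separate a deficit from the same angle past neutral: the error is twice the deficit, change is reversed while the foot stays below neutral, and change can cancel when the foot crosses it. Taken as a direction convention, it leaves deficits to each assessor.

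How many participants this touches cannot be found from the protocol, and the SD and sample-size ranges above rest wholly on assumed means and SDs. The effect is confined to the mean, change and SD of ankle range, and would reach a future sample size only if that outcome were chosen. Consent, retention and adherence criteria are untouched.

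The mixed TUG pace instruction is a separate wording fault of unknown size. Both are minor matters of measurement standardisation.

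**What to change.** 1. In Section 7.4.6.3, add that dorsiflexion not reaching neutral is recorded as a negative value, for example −10°. Use the same convention in the clinical test pack and the CRF. If the pack already has a code, make the two agree.
2. In Section 7.4.6.7, reduce the script to one pace instruction and delete the other.

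The cost is two sentences and no new procedure. If baseline visits have begun, query the ankle values already recorded, because the sign cannot be recovered from the number alone.

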7.4.6.4 MRC Oxford strength assessment (Knee and ankle)

- The Oxford Scale is a quick method of assessing and grading muscle power.
- The Oxford Scale is a 0-5 scale which is then recorded as 0/5 or 2/5.
- Only whole numbers should be used for the assessment e.g. **no** use of + or - sign qualifiers should be used.
- The researcher should position the participant in the appropriate posture to allow accurate assessment and allow good vision and palpation of the appropriate structures.
- The muscles will be tested isometrically, usually in their mid-range and **NOT** through range.
- The movements being evaluated are
 - Knee extension strength
 - Knee flexion strength
 - Ankle dorsiflexion strength
 - Ankle plantarflexion strength
- This is achieved by positioning
 - Ankle joint in neutral (foot orthogonal to the shank)
 - Knee in 90° of flexion.
- The position of the limb may be adjusted to elicit a better contraction from the muscle group being tested.
- Instruct the participant that you are going to apply some resistance to the limb and that you want them to resist you.
- Verbal encouragement is allowed.
- A maximum of up to three tests are allowed, with the highest value being recorded.
- A score is awarded based on the criteria below

Level	Description
0	No contraction at all
1	Flicker of contraction only (visible/palpable muscle contraction), movement of the joint does not occur
2	movement is possible only with gravity and the weight of the limb counterbalanced
3	Movement against gravity only

4	Movement against gravity with some resistance
5	Movement against gravity with full resistance

7.4.6.5 Modified Ashworth test (MAS)

The modified Ashworth test will be used to assess the stiffness of the flexors and extensors of the knee and ankle joints.

- Legs and joints scored independently

Instructions for carrying out the test

- These may be conducted with the participant sitting.
- If a plinth, bed or appropriate piece of equipment is present that allows the participant to lie down in supine.
- The participant should be relaxed during the testing.
- The test may be done for a maximum of 3 times for each muscle group.
- When testing a muscle that primarily flexes a joint, place the joint in a maximally flexed position and move to a position of maximal extension over one second (count “one thousand one”).
- When testing a muscle that primarily extends a joint, place the joint in a maximally extended position and move to a position of maximal flexion over one second (count “one thousand one”).

The muscle groups to be assessed are for both the left and right legs are

- Knee joint through flexion – from fully extended to flexed
 - assessing knee extensors (quads)
- Knee through extension – from fully flexed to extended
 - assessing knee flexors – (hamstrings)
- Ankle joint through plantar flexion – from fully dorsiflexed to plantar flexed
 - ankle dorsiflexors (tib ant and toe extensors)
- Ankle joint through dorsi flexion - from fully plantar flexed to dorsi flexed
 - ankle plantar flexors (triceps surae and toe flexors)

A score is awarded based on the criteria below

Score	Descriptor
0	No increase in muscle tone
1	Slight increase in muscle tone, with a catch and release or minimal resistance at the end of the range of motion when an affected part(s) is moved in flexion or extension
1+	Slight increase in muscle tone, manifested as a catch, followed by minimal resistance through the remainder (less than half) of the range of motion
2	A marked increase in muscle tone throughout most of the range of motion, but affected part(s) are still easily moved
3	Considerable increase in muscle tone, passive movement difficult
4	Affected part(s) rigid in flexion or extension

7.4.6.6 Common equipment needed for Timed up and Go and 2MWT (clinical measures)

Required equipment (clinician)

- stopwatch
- two small cones to mark the turnaround points
- worksheets on a clipboard
- a measuring wheel
- telephone
- a source of oxygen
- sphygmomanometer
- automated electronic defibrillator

Required equipment (participant)

- Participants should use their usual walking aids during the test (cane, walker, etc.).

Safety considerations

1. Testing should be performed in a location where appropriate response to an emergency is possible. The appropriate location of a crash cart should be determined by the person supervising the facility.
2. Supplies that must be available include oxygen, sublingual nitroglycerine, aspirin, and albuterol (metered dose inhaler or nebulizer). A telephone or other means should be in place to enable a call for help.
3. The researcher collecting the measurements should be certified in cardiopulmonary resuscitation with a minimum of Basic Life Support. A certified individual should be readily available to respond if needed.
4. Medical doctors are not required to be present during the test. The Principal Investigator after consultation with the wider research team may decide whether attendance by a medical doctor at a specific test is required.
5. If a participant is on chronic oxygen therapy, oxygen should be given at their standard rate or as directed in their medical care plan.

Reasons for immediately stopping a TUG or 2MWT include the following:

1. chest pain,
2. intolerable dyspnea,
3. leg cramps,
4. staggering,
5. diaphoresis (excessive or abnormal sweating for no apparent reason) and
6. pale or ashen appearance.

The researcher must be trained to recognize these problems and the appropriate responses. If a test is stopped for any of these reasons, the participant should sit or lie supine as appropriate depending on the severity or the event and the researcher's assessment of the severity of the event and the risk of syncope. The following should be obtained based on the judgment of the technician: blood pressure, pulse rate, oxygen saturation, and a physician evaluation. Oxygen should be administered as appropriate.

7.4.6.7 Timed up and Go (clinical measure)

Adapted from Podzialdo and Richardson 1991 ⁴⁵

Required equipment (clinician)

- stopwatch
- a chair that can be easily moved along the walking course
- 3.5 m hallway
- 30 m walkway

Location

- The Timed up and Go should be performed indoors, along a long, flat, straight, enclosed space with a hard surface. For the test, avoid corridors or spaces that are busy, used by lots of other people and have a high volume of footfall.
- Place a standard height chair at the beginning of the walkway

[figure not shown]

Image taken from Emerson Sebastião et al 2016 ⁴⁶

Measurement (carrying out the test)

- A “warm-up” period before the test is not required.
- A practice round may be performed if required but ensure that the participant has adequate time after this to recover.
- The participant should sit at rest in a chair, located near the starting position, for at least 10 minutes before the test starts.
- During this time make sure that clothing and shoes are appropriate.

Instructions for carrying out the test

1. The participant should sit on a standard armchair, placing their back against the chair and resting their arms chair's arms.
2. The upper extremities should not be on the assistive device (if used for walking), but it should be nearby.
3. Regular footwear and customary walking aids should be used.
4. Instruct the participant as follows:

- *The aim of this test is to assess the way you walk and balance.*
- *The test will start when I say Go.*
- *From sitting you will stand up, walk to the line/ cone that is 3 meters way, turn around at the line/cone walk back to the chair and sit down.*
- *I will stop the timer when your buttocks touch the seat*
- *The aim of the test is to see how fast you can do this but “You should walk at a comfortable and safe walking speed.”*

5. Demonstrate the test to the participant.
6. A stopwatch should be used to time the test (in seconds).
7. When the participant is ready say

“Go”

8. Start the stopwatch

9. Do not talk to anyone during the walk. Use an even tone of voice if required to instruct the participant.

7.4.6.8 Two-minute walk test (2MWT) (clinical measure)

Instructions adapted from the ATS statement: guidelines for the six-minute walk test.⁶⁴

Required equipment (clinician)

- countdown timer (or stopwatch)
- mechanical lap counter
- a chair that can be easily moved along the walking course
- 30.5 m hallway.
- 30 m walkway
- markings on floor

Location

- The 2MWT should be performed indoors, along a long, flat, straight, enclosed corridor with a hard surface. For the test, avoid corridors or spaces that are busy, used by lots of other people and have a high volume of footfall.
- The walking course must be 30 m in length. A 30.5 m hallway is, therefore, required.
 - In relation to the 6MWT from which the 2MWT is adapted, most 6MWT studies have used a 30-m corridor⁶⁵, but some have used 20- or 50-m corridors.^{66,67}
 - A multicenter study found no significant effect of the length of straight courses ranging from 15 to 50m, but patients walked farther on continuous (oval) tracks (mean 92m farther).⁶⁸
- The length of the corridor should be marked every 3 m.
- The turnaround points should be marked with a cone (such as an orange traffic cone).
- A starting line, which marks the beginning and end of each 60-m lap, should be marked on the floor using brightly coloured tape.

[figure not shown]

Image taken from Benavent-Caballer (2016) ⁶⁹

Measurement (carrying out the test)

- A “warm-up” period before the test should not be performed.
- Participants are allowed to stop and rest during the test.
- The participant should sit at rest in a chair, located near the starting position, for at least 10 minutes before the test starts.
- During this time, researcher may adjust the space for the setup of the 2MWT.

After the test

1. Record the time taken to complete the timed up and Go.
2. Congratulate the participant on good effort and offer a drink of water.

Instructions for carrying out the test

1. Set the lap counter to zero and the timer to 2 minutes.
2. Assemble all necessary equipment (lap counter, timer, clipboard, worksheet) and move to the starting point.
3. Instruct the participant as follows:

- *“The object of this test is to walk as far as possible for 2 minutes.*
- *Walk continuously, if possible, but do not be concerned if you need to slow down or stop to rest.*
- *The goal is to feel at the end of the test that more ground could not have been covered in the 2 minutes.*
- *You may lean against the wall while resting or we can provide a chair if required but resume walking as soon as you are able.*
- *You will be walking back and forth around the cones.*

- ***Now I'm going to show you. Please watch the way I turn without hesitation.”***
 - *Demonstrate by walking one lap yourself. Walk and pivot around a cone briskly.*

- *“Are you ready to do that? I am going to use this counter to keep track of the number of laps you complete. I will click it each time you turn around at this starting line.*
- ***Remember that the object is to walk AS FAR AS POSSIBLE for two minutes, but don't run or jog.***

- *Start now, or whenever you are ready.”*

4. Position the participant at the starting line. You should also stand near the starting line during the test. Do not walk with the participant unless support is required. As soon as the participant starts to walk, start the timer.
5. Do not talk to anyone during the walk. Use an even tone of voice when using the standard phrases

of encouragement. Watch the participant. Do not get distracted and lose count of the laps. Each time the participant returns to the starting line, click the lap counter once (or mark the lap on the worksheet). Let the participant see you do it. Exaggerate the click using body language, like using a stopwatch at a race.

- After the first minute, tell the participant the following (in even tones):

“You are doing well. You have 1 minute to go.”

- When the timer shows only 30 seconds remaining, tell the participant:

“You are doing well. You have only 30 seconds to go.”

- Do not use other words of encouragement (or body language to speed up).
- When the timer is 15 seconds from completion, say this:

“In a moment I’m going to tell you to stop. When I do, just stop right where you are and I will come to you.”

- When the timer rings (or buzzes), say this:

“Stop!”

- Walk over to the participant. Consider taking the chair if they look exhausted. Mark the spot where they stopped by placing a bean bag or a piece of tape on the floor.

After the test

3. Post-test: ask this:

“What, if anything, kept you from walking farther?”

4. If using a pulse oximeter, measure SpO₂ and pulse rate from the oximeter and then remove the sensor.
5. Record the number of laps from the counter (or tick marks on the CRF).
6. Record the additional distance covered (the number of meters in the final partial lap) using the markers on the wall as distance guides. Calculate the total distance walked, rounding to the nearest meter, and record it on the CRF.
7. Congratulate the participant on good effort and offer a drink of water.

